3.3 Number of Participants to be Enrolled

3.3.1 Proposed sample size

This study will enroll a minimum of 3 participants and a maximum of 36 participants (planned enrollment of 18 participants with HIV infection and 18 participants without HIV infection).

3.3.2 Accrual rate

Approximately 1-2 participants per month.

3.4 Participant Enrollment Procedures

Sites must have this protocol approved by their Institutional Review Boards (IRB) and be registered for study participation with the AIDS Malignancy Consortium (AMC) Operations and Data Management Center (ODMC) before they may enroll participants. Enrollment and data collection will occur via Advantage eClinical.

3.4.1 Registration for screening

After an informed consent form has been signed by the participant and the protocol-

specific eligibility checklist for Segment A has been completed, the participant must be registered for screening (AMC-098, Segment A, Screening Enrollment) on-line via Advantage eClinical. After successful registration into screening, the participant will receive an eleven-digit participant ID and will then enter the screening process (screening and pre-entry visits). A system generated confirmation email will be sent to the enroller upon successful completion of the participant enrollment into Segment A. If the on-line system is inaccessible, the site should notify the AMC ODMC (via email at [contact] or via phone at [contact]) for further instructions.

3.4.2 Enrollment

After the screening evaluations have been obtained and the participant is determined to be eligible, the participating site will enroll the participant into AMC-098 Segment B (Treatment Enrollment) on-line via Advantage eClinical. Enrollment into Segment B should occur no more than 1 week prior to administration of the first dose of the protocol agent (enrollment 1 day prior to or on the day of treatment is strongly encouraged).

Participants must be enrolled into AMC-098 Segment B (Treatment Enrollment) prior to receiving the first dose of the protocol agent.

3.5 Enrollment at International Sites

Enrollment is open at all sub-Saharan Africa AMC international sites contingent upon site satisfaction of all regulatory and site activation requirements.

4.0 TREATMENT PLAN

4.1 Agent Administration

The protocol agent will be administered on an outpatient basis. A cycle is 2 weeks of continuous treatment (+/- 3 days according to timing of study visit/evaluations within window). Reported adverse events and potential risks for nelfinavir are described in [Section 6.0](#). Appropriate dose modifications for nelfinavir are described in [Section 5.0](#). No investigational or commercial agents or therapies other than those described below may be administered with the intent to treat the participant's malignancy.

All participants will initiate protocol treatment with nelfinavir 1250 mg BID continuously for up to 8 weeks, and then, depending on response at the standard dose, advance to high dose nelfinavir at 3125 mg BID continuously (i.e., intrapatient dose escalation) for up to 16 weeks (up to 24 weeks of treatment).

NOTES: The participant will be requested to maintain a medication diary of each dose of medication (See [Appendix VII](#)). The medication diary will be returned to clinic staff at the end of each cycle (every two-week study visit).

The site will be required to document study agent return by participant in source documents. Non-compliance with study agent administration should be noted at the time of diary collection and the participant should be instructed again regarding dosing instructions.

Dose delays and modifications for participants experiencing toxicity are described in [Section 5.0](#). Due to the known food-effects on the bioavailability of nelfinavir, clinical staff will provide nutritional counseling for agent administration to ensure that the participant is aware the drug must be consumed with a moderately-high fat meal, to increase absorption and decrease pharmacokinetic variability, and that acidic foods/fruit juices are avoided at time of administration.

Treatment intensification will depend on the response at each treatment level:

4.1.1 Standard dose nelfinavir (1250 mg BID)

- Each participant must be observed for a minimum period of at least 4 weeks on standard dose nelfinavir before escalation to the high dose nelfinavir treatment level.
- If after 4 weeks there is progressive disease (PD), the participant will advance to the high dose nelfinavir level.
- If by 8 weeks there is stable disease (SD) or partial response (PR) at the standard dose, the participant will advance to the high dose level.
- If there is complete response (CR) at any time at the standard dose level, nelfinavir will be discontinued 4 weeks after documentation of complete response.
- Because dosing of study drug is continuous both during and between cycles, care should be taken to avoid study drug interruption. Therefore, if the study visit/study evaluations occur within the +/- 3 day visit window, the appropriate

amount of drug should be provided at that visit for the study interval (i.e., if the study visit occurs 3 days before the 14th day of the cycle, the sufficient drug should be provided to prevent to last 17 days, or until the date of next scheduled visit)

4.1.2 High dose nelfinavir (3125 mg BID)

- High dose nelfinavir treatment will be continued for at least 4 weeks.
- If there is progressive disease (PD) documented after 4 weeks at the high dose level, nelfinavir will be discontinued.
- If there is stable disease (SD) or partial response (PR) at the high dose level, high dose nelfinavir will be continued for up to 16 weeks.
- If there is a complete response (CR), high dose treatment will be discontinued 4 weeks after documentation of complete response.

4.2 General Concomitant Medication and Supportive Care Guidelines

Because there is a potential for interaction of nelfinavir with other concomitantly administered drugs through the cytochrome P450 system, the case report form must capture the concurrent use of all other drugs, over-the-counter medications, or alternative therapies. A patient drug information and wallet card for potential drug-interactions will be provided to participants (See [Appendix XIV](#)). The site Principal Investigator should be alerted if the participant is taking any agent known to affect or with the potential to affect selected CYP450 isoenzymes. Questions regarding ART regimens may be directed to [name]. [Appendix XI](#) presents guidelines for identifying medications/substances that could potentially interact with the study agent.

Antiretroviral therapy is required for HIV-infected participants, with the stipulations detailed in [Section 3.1.8](#). Participants may not have received a PI for at least 4 weeks prior to enrollment. Management of HIV will be left to the discretion of the investigator. Modification of antiretroviral therapy to eligible antiretroviral drugs is allowed after study entry and will be made at the discretion of the investigators. Any changes to antiretroviral therapy must be documented in the case report form (CRF).

4.3 Duration of Therapy

In the absence of treatment delays due to adverse event(s), treatment may continue for a minimum of 8 weeks as per [Section 4.1](#) or until one of the following criteria in [Section 4.5](#) applies.

4.4 Duration of Follow Up

All participants will be followed for 8 weeks after removal from study or until death, whichever occurs first. Participants removed from study for unacceptable adverse event(s) (see [Section 4.5](#)) will be followed until resolution or stabilization of the adverse event(s).

4.5 Criteria for Removal from Treatment

Participants will be removed from study treatment according to the criteria listed in [Section 5.0](#). The reason for study treatment removal and the date the participant was removed must be documented in the Case Report Form in Advantage eClinical.

- Disease progression after 4 weeks on high dose nelfinavir;
- Rapid progression of disease that is deemed to be life-threatening;
- Intercurrent illness that prevents further administration of treatment;
- Unacceptable adverse event(s);
- Participant decides to withdraw from the study;
- General or specific changes in the participant's condition render the participant unacceptable for further treatment in the judgment of the investigator;
- Participants who become pregnant or need to breast-feed;
- The Investigator has the right to remove participants from the study for clinical reasons which he/she believes are life threatening to the participant even if such reasons do not fall into the toxicity classifications discussed in [Section 5.0](#);
- Participants requiring a cumulative delay of > 2 weeks (i.e., across cycles) or, participants requiring > two dose reduction (i.e., requiring reduction to < 1875 mg BID) throughout the duration of the study.

5.0 DOSING DELAYS/DOSE MODIFICATIONS

5.1 Dose Modifications for Nelfinavir

There will be no dosage modifications for participants receiving standard dose nelfinavir (1250 mg BID) as this dose is currently FDA approved for treatment of HIV infection and has been studied extensively in Phase I-IV studies, with clinical experience over the last two decades⁶⁵⁻⁶⁷.

If at any time during administration of standard dose nelfinavir (1250 mg BID) the participant experiences an adverse event at a severity (grade) that requires dose interruptions per the tables below, study treatment will be terminated.

Unless noted otherwise for a specific event, if at any time during administration of high dose nelfinavir (3125 mg BID) the participant experiences an adverse event grade that requires dose interruptions per the tables below, study drug will be held until the event resolves or improves to the specified grade, and then reduced by 625 mg BID (at 2500 mg BID) and continued as above unless the adverse event recurs, in which case the dose is reduced by another 625 mg to a minimum of 1875 mg BID if required. If the participant experiences an adverse event on high dose nelfinavir that does not resolve or improve to the specified grade after reducing the dose to 1875 mg BID, study treatment will be terminated.

If any participant requires a cumulative treatment delay of > 2 weeks throughout the duration of the study (i.e. total across cycles), then the participant must discontinue study treatment.

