5.1.2 Tables of adverse events, and indications for dose modifications and management

The AEs and corresponding severity definitions below are as classified in the NCI Common Terminology Criteria for Adverse Events (CTCAE), version 5.0, as required in protocol [Section 6.0](#).

Event Name	Nausea	
Grade of Event	Management/Next Dose for Standard Dose- Nelfinavir	Management/Next Dose for High Dose- Nelfinavir
≤ Grade 1	No change in dose	No change in dose
Grade 2	No change in dose	No change in dose
Grade 3	Hold* until ≤ Grade 1. Resume at same dose level.	Hold* until ≤ Grade 1. Resume at one dose level lower, if indicated.**
Grade 4	Off protocol therapy	Off protocol therapy
*Participants requiring a cumulative delay of > 2 weeks should go off protocol therapy. **Participants requiring > two dose reductions should go off protocol therapy.		
Recommended management: antiemetics.		

Event Name	Vomiting	
Grade of Event	Management/Next Dose for Standard Dose-Nelfinavir	Management/Next Dose for High Dose-Nelfinavir
≤ Grade 1	No change in dose	No change in dose
Grade 2	Hold until ≤ Grade 1. Resume at same dose level.	Hold until ≤ Grade 1. Resume at same dose level.
Grade 3	Hold* until < Grade 2. Resume at same dose level.	Hold* until < Grade 2. Resume at one dose level lower, if indicated.**
Grade 4	Off protocol therapy	Off protocol therapy
*Participants requiring a cumulative delay of > 2 weeks shall go off protocol therapy. **Participants requiring > two dose reductions shall go off protocol therapy.		
Recommended management: antiemetics.		

Event Name	Diarrhea	
Grade of Event	Management/Next Dose for Standard Dose-Nelfinavir	Management/Next Dose for High Dose-Nelfinavir
≤ Grade 1	No change in dose	No change in dose
Grade 2 considered tolerable or easily managed	Add supportive care as indicated. No change in dose.	Add supportive care as indicated. No change in dose.
Grade 2 considered intolerable to participant or deemed unacceptable in the investigator's judgment	Hold until ≤ Grade 1. Resume at same dose level.	Hold until ≤ Grade 1. Resume at same dose level.
Grade 3	Hold* until ≤ Grade 2 if tolerable, or ≤ Grade 1 if considered intolerable at Grade 2. Resume at same dose level.	Hold* until ≤ Grade 2 if tolerable, or ≤ Grade 1 if considered intolerable at Grade 2. Resume at one dose level lower, if indicated. **
Grade 4	Off protocol therapy	Off protocol therapy

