
*Participants requiring a cumulative delay of >2 weeks shall go off protocol therapy.
 
**Participants requiring > two dose reductions shall go off protocol therapy.
		

Recommended management: loperamide antidiarrheal therapy.
 
Dosage schedule: 4 mg at first onset, followed by 2 mg with each loose motion until diarrhea-free for 12 hours (maximum dosage: 16 mg/24 hours).
 
Adjunct anti-diarrheal therapy is permitted and shall be recorded when used.
		

Event Name	Neutropenia	
Grade of Event	Management/Next Dose for Standard Dose-Nelfinavir	Management/Next Dose for High Dose-Nelfinavir
≤ Grade 1	No change in dose	No change in dose
Grade 2	No change in dose	No change in dose

Event Name	Neutropenia	
Grade of Event	Management/Next Dose for Standard Dose-Nelfinavir	Management/Next Dose for High Dose-Nelfinavir
Grade 3	Hold* until \leq Grade 2. Resume at same dose level.	Hold* until \leq Grade 2. Resume at one dose level lower, if indicated. **
Grade 4	Off protocol therapy	Off protocol therapy

*Participants requiring a cumulative delay of > 2 weeks shall go off protocol therapy.
**Participants requiring $>$ two dose reductions shall go off protocol therapy.

Event Name	Thrombocytopenia	
Grade of Event	Management/Next Dose for Standard Dose-Nelfinavir	Management/Next Dose for High Dose-Nelfinavir
\leq Grade 1	No change in dose	No change in dose
Grade 2	Hold until \leq Grade 1. Resume at same dose level.	Hold until \leq Grade 1. Resume at same dose level.
Grade 3	Hold* until \leq Grade 1. Resume at same dose level.	Hold* until \leq Grade 1. Resume at one dose level lower, if indicated. **
Grade 4	Off protocol therapy	Off protocol therapy

*Participants requiring a cumulative delay of > 2 weeks shall go off protocol therapy.
**Participants requiring $>$ two dose reductions shall go off protocol therapy.

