10.2 Sample Size/Accrual Rate

The study is designed to test the null hypothesis that the response rate is less than or equal to 20% against the alternative that it is 40% or greater with 90% power at a one-sided 10% significance level which will require a sample size of 36 evaluable participants using the exact test for a single proportion^{3,4}.

The plan is to enroll 18 participants who are HIV-positive and 18 who are HIV-negative, at an estimated accrual rate of 1-2 participants/month. Participants from both the international and domestic sites will contribute to the single analysis plan, which is based on HIV status and not site of recruitment.

Evaluable participants for all endpoints are defined as participants who meet all the eligibility criteria, enroll on the study, and receive at least one dose of treatment. Participants who enroll but are not treated will be replaced.

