10.4 Stopping Rule for Feasibility

The stopping rule is based on an underlying proportion of participants with adverse events that require treatment termination of 0.05. Thus, the stopping rule is derived by determining the number of participants with adverse events that require treatment termination which would occur $\leq 5\%$ of the time of the true underlying rate of treatment terminations due to adverse events was 0.05. The trial will be stopped if the number of participants who terminate treatment due to adverse events is greater than or equal to X out of N participants:

X	N
2	3-7
3	8-16
4	17-28
5	29-36

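### Section 5.1 ends treatment for any standard-dose adverse event that requires a dose interruption, but eight standard-dose cells in Section 5.1.2 say hold and resume, and the supplied documents do not say which governs

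*Combined protocol and SAP*

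**What the plan says.** Section 5.1 has separate paragraphs for the two dose levels. The standard-dose paragraph (1250 mg BID) says that if a participant "experiences an adverse event at a severity (grade) that requires dose interruptions per the tables below, study treatment will be terminated". The high-dose paragraph uses the same notion of a dose interruption but prescribes a hold followed by dose reduction. It alone opens with an exception for events where something else is noted. The last paragraph of Section 5.1 covers both doses: "If any participant requires a cumulative treatment delay of > 2 weeks throughout the duration of the study", treatment must be discontinued.

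Section 5.1.2 then gives five tables, each with its own standard-dose column. For grade 3 nausea that column reads "Hold* until ≤ Grade 1. Resume at same dose level". The asterisk leads to a footnote, worded in the diarrhea table as "Participants requiring a cumulative delay of >2 weeks shall go off protocol therapy". Grade 4 is marked as off protocol therapy in every table.

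Section 4.5 sends the reader back to Section 5.0 for removal criteria and repeats the two-week limit. Section 10.4 states: "The trial will be stopped if the number of participants who terminate treatment due to adverse events is greater than or equal to X". The limit X rises with the number of participants N. Section 10.2 defines evaluable participants as eligible people who "enroll on the study, and receive at least one dose of treatment".

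**The concern.** The sentence in Section 5.1 and the tables it cites give opposite instructions for the same event. A participant with grade 2 vomiting on 1250 mg BID goes off treatment under the sentence and is held, then resumed, under the table. A site cannot do both.

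Three things depend on the answer:

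- **Exposure.** A participant taken off treatment never reaches the high-dose phase, which is part of the escalation strategy named in the primary objective.
- **The stopping count.** A termination for an adverse event counts toward the Section 10.4 limits, which are low (2 to 5). A hold that resolves does not count.
- **The primary analysis.** The participant stays in the response denominator after one dose. A partial or complete response already reached on standard dose can still count, but the chance to respond on high dose is lost.

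**Working it through.** **Step 1: the conflicting cells.** These are all the standard-dose entries in Section 5.1.2 that call for a hold and a return to the same dose.

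| Event | Grade | Two-week asterisk |
|---|---|---|
| Nausea | 3 | yes |
| Vomiting | 2 | no |
| Vomiting | 3 | yes |
| Diarrhea | 2, intolerable | no |
| Diarrhea | 3 | yes |
| Neutropenia | 3 | yes |
| Thrombocytopenia | 2 | no |
| Thrombocytopenia | 3 | yes |

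Count: 1 + 2 + 2 + 1 + 2 = 8 cells, of which 5 carry the asterisk. Five are gastrointestinal and three are blood-count cells. Section 8.2.5 and Appendix I schedule no blood count during standard dose, so the conflict falls mainly on the five gastrointestinal cells.

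**Step 2: can the two rules be reconciled?**

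- Reading a dose interruption as grade 4 only fails. Grade 4 is already off therapy, and the high-dose paragraph uses the same phrase for a hold.
- The exception clause belongs to the high-dose paragraph only.
- The statement that standard dose is not modified fits either rule, because resuming at 1250 mg is not a dose change.
- Section 4.5 points back to Section 5.0, so it cannot break the tie.

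**Step 3: the stopping rule.** The limits are 2 (N 3–7), 3 (N 8–16), 4 (N 17–28) and 5 (N 29–36), built on a 5% termination rate. First, the plan's own table. P(Bin(N, 0.05) ≥ X) at the end of each row is 0.0444 (2 of 7), 0.0429 (3 of 16), 0.0491 (4 of 28) and 0.0324 (5 of 36). All are at or below 0.05, so the table agrees with its stated derivation.

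Next, the chance of ever crossing a limit, by exact binomial recursion with a check after each participant from the 3rd to the 36th:

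| Total termination rate | P(cross a limit) |
|---|---|
| 3% | 2.9% |
| 5% | 9.7% |
| 6% | 14.8% |
| 7% | 20.8% |
| 8% | 27.5% |

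The documents give no rate of standard-dose interruptions, so the rates other than 5% are assumptions. Which rows apply depends on what the 5% covers, and Section 10.4 does not say:

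- If it leaves out terminations caused only by the Section 5.1 sentence, adding 1, 2 or 3 points moves 5% to 6%, 7% or 8%.
- If it includes them, following the tables moves the rate down. For example, with 2 points due to the sentence, 5% − 2% = 3%.

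A participant who would terminate for an adverse event under either rule counts once both ways and changes nothing.

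**Step 4: the primary test.** Section 10.1 rejects the null at 11 or more responders of 36. P(Bin(36, 0.20) ≥ 11) = 0.0889 and P(Bin(36, 0.40) ≥ 11) = 0.9096, in line with the stated 10% one-sided level and 90% power. Suppose a fraction q is terminated by the sentence and cannot respond. The response rate π becomes π(1 − q):

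| q | Power, π = 0.40 | Type I error, π = 0.20 |
|---|---|---|
| 0 | 91.0% | 8.9% |
| 1% | 90.1% | 8.4% |
| 2% | 89.3% | 7.9% |
| 3% | 88.4% | 7.4% |

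These figures ignore early stopping. At q of 1% to 3%, the expected number affected is 0.36 to 1.08 of 36.

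**The case against.** The best defence is that this is a drafting slip with an obvious answer. The tables have a dedicated standard-dose column that separates holds from grade 4 removal, and five of the eight holds carry a two-week limit that would do nothing if every hold meant termination. This stands as evidence of intent, but it is not a written order of precedence. The separate standard-dose and high-dose paragraphs, with different consequences, could also be deliberate. A reader might infer that the tables govern as a matter of text. The supplied documents do not say so.

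A second defence is rarity. Section 2.2.1 reports no grade 3 or 4 diarrhea in a trial of 625 and 1250 mg BID, and diarrhea in 2–11% of participants in sub-Saharan African trials without need to discontinue. Section 7.1.11 lists vomiting and thrombocytopenia among events in under 2%. This stands: the number affected may be small. It limits the damage but does not settle what a site should do.

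A third defence is central oversight. Appendix VI provides medical-monitor review of adverse events and central determination of phase II stopping criteria. That may limit divergence between sites, and the documents do not show that sites have diverged. It does not correct the instruction.

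Two stronger readings are tempting and unsupported:

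- **That the Section 5.1 sentence must raise the chance of stopping above 9.7%.** This holds only if the 5% leaves such terminations out.
- **That the power loss has a floor at 79.5%,** from P(Bin(32, 0.40) ≥ 11) with four non-responding terminations, on the ground that a fifth would stop the trial. Section 10.4 does not say that stopping removes the response analysis, and a fifth termination can come after all 36 are enrolled. Five give P(Bin(31, 0.40) ≥ 11) = 75.5%. Both figures are conditional on an assumed count with no responder among those terminated, so neither belongs beside the power figures in Step 4.

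**Conclusion.** The contradiction is certain on the text supplied and should be fixed. Some pages were removed before review and the manual of procedures was not supplied, so the absence of a precedence rule is a statement about the supplied documents only. The tables are the more likely intent.

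The size is uncertain and may be small. The point rests on two opposite instructions for the same event, which decide who reaches high dose and who counts in Section 10.4. It does not rest on the assumed rates. Those rates show that the stopping rule is sensitive to a few extra or fewer terminations, in a direction that depends on what the 5% covers. The effect on power is minor, and type I error is not inflated.

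**What to change.** Replace the standard-dose sentence in Section 5.1 with:

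> If the tables below require a hold during standard dose nelfinavir, hold study drug and resume at 1250 mg BID as the table directs. Study treatment is terminated for an event marked Off protocol therapy, if the cumulative delay exceeds 2 weeks, or as specified in Section 4.5.

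If the clinical team does intend termination, keep the sentence, change the eight cells to off protocol therapy, and remove the asterisk from the five that carry it. Leave Section 10.4 as written, so that adverse-event terminations without a table still count.

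**Cost.** Section 12.2 requires a written amendment with CTEP and investigator approval and IRB/IEC approval, so a site memo alone will not do. The change is short and can go with the next amendment. Sample size, stopping limits, visits and procedures stay the same.

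**Downside.** If the tables govern, standard-dose events that are held and resolve will not count toward the Section 10.4 limits. The clinical team should accept that knowingly.
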